5.6. Interim Analyses

Up to 2 interim analyses were planned for Study CGAL. Interim analysis 1 during SP III may be conducted that may result in increasing the sample size or stopping the trial for futility. Details were documented in the Statistical Analysis Center SAP, ERB supplement, and DMC Charter. However, this interim analysis for sample size re-estimation will not happen due to enrollment infeasibility. The DMC will still independently monitor patient safety during this trial.

The other interim analysis that was planned will be conducted after all patients have had the opportunity to complete 8 weeks of treatment (SP III) and, thus, will be the final analysis of the primary efficacy endpoint. The interim analysis will be conducted using internal unblinded study team members who do not have direct interaction with sites.

5.7. Unblinding Plan

Interim analysis will be conducted by unblinded study team members who do not have direct interaction with sites. All study personnel with direct interaction with sites are kept blinded to individual patient treatment information.

5.8. Reports to Be Generated at Each Interim and Final Database Lock

5.8.1.1. Reports to Be Generated at Interim Database Lock

For the interim analysis, the database will be locked after all randomized patients have had the chance to complete 8 weeks of treatment in SP III. However, some patients will still be ongoing in SP IV at the time of the database lock. Data up to the data cutoff date in the locked database from all study phases will be used, and analyses specified in this SAP will be performed. However, only analyses conducted for SP III at interim analysis will be considered as the final

analyses. The analyses including data from SP IV will be rerun and updated when the completed data are available at the final database lock.

5.8.1.2. Reports to Be Generated at Final Database Lock

For final database lock, all analyses including tables, figures and listings that use data from SP IV will be generated.

5.9. Clinical Trial Registry Analyses

Additional analyses will be performed for the purpose of fulfilling the Clinical Trial Registry (CTR) requirements. These analyses will be the responsibility of the Sponsor.

Analyses provided for the CTR requirements include the following:

A summary of AEs will be provided as a dataset that will be converted to an XML file. Both Serious Adverse Events and “Other” Adverse Events are summarized by treatment group and by MedDRA PT.

- An AE is considered “Serious” whether or not it is a TEAE.
- An AE is considered in the “Other” category if it is both a TEAE and is not serious. For each “Serious” AE and “Other” AE, for each term and treatment group, the following are provided:
 - the number of participants at risk of an event
 - the number of participants who experienced each event term
 - the number of events experienced
- Consistent with www.ClinicalTrials.gov requirements, “Other” AEs that occur in fewer than 5% of patients in every treatment group may not be included if a 5% threshold is chosen.
- AE reporting is consistent with other document disclosures; for example, the CSR, manuscripts, and so forth.

6. References

Guy W. ECDEU assessment manual for psychopharmacology, revised 1976. Rockville, MD: National Institute of Mental Health, Psychopharmacology Research Branch. p 217-222. Available at: <https://archive.org/details/ecdeuassessmentm1933guyw>. Accessed September 29, 2014.

Permutt T. Sensitivity analysis for missing data in regulatory submissions. *Stat Med*. 2015;35(17):2876-2879.

Appendix 1. Description of Important Protocol Deviations

Category	Subcategory	Study Specific Term	Source
Informed Consent Form (ICF)	Informed consent not obtained		Programmable
	Improper consent	ICF not signed prior to initiation of protocol procedures	Nonprogrammable
Eligibility	Inclusion/Exclusion	At Visit 1 patients must have a history of episodic cluster headache	Nonprogrammable
		Age < 18 or > 65 years old at study entry	Nonprogrammable
		Female patients who have a positive serum pregnancy test prior to Visit 3	Programmable
		Randomized patients had prior or current exposure to CGRP antibody	Nonprogrammable
		Corrected QT (QTcB) interval > 470 msec for women and >450 for men prior to Visit 3	Nonprogrammable
		PR > 220, or conduction delay of QRS>120 prior to Visit 3	Nonprogrammable
		SBP >160 mm Hg or DBP >100 mm Hg on 2 or more blood pressure assessments prior to Visit 3	Programmable
		Evidence of ischemia /qualitative findings of ST or J-point elevation, excluding early repolarization	Nonprogrammable
		History of MI, UA, PCI, CABG, or DVT/PE within 6 months of screening	Nonprogrammable
		Have planned cardiovascular surgery or percutaneous coronary angioplasty	Nonprogrammable

Category	Subcategory	Study Specific Term	Source
Eligibility	Inclusion/ Exclusion	Any lifetime history of vasospastic angina or stroke	Nonprogrammable
		Clinical evidence of peripheral vascular disease or a diagnosis of Raynaud's Phenomenon	Nonprogrammable
		Have any history of intracranial or carotid aneurysm, intracranial hemorrhage, stroke	Nonprogrammable
		Have a history of intracranial tumors or significant head trauma that preclude study participation	Nonprogrammable
		Have a clinically significant elevation of ≥ 2 X ULN for ALT, or ≥ 1.5 X ULN for TBIL or ALP prior to V3	Nonprogrammable
		Have a positive urine drug screen for substances of abuse not allowed prior to randomization	Programmable
		Completion of less than 5 of 7 days of the daily ePRO diary during the baseline assessment	Programmable
		Baseline weekly cluster headache attack: (a) ≥ 2 consecutive days without attack, or (b) < 4 total attacks, or (c) > 8 attacks per day	Programmable
		Body mass index (BMI) ≥ 40 kg/m ² at baseline.	Programmable
		Use within 14 days prior to SP II or in SP II/III of any of the medications described in I/E 9a	Programmable
		Use within 30 days prior to SP II or in SP II/III of any of the medications described in I/E 9b	Programmable

Category	Subcategory	Study Specific Term	Source
Study Procedures	Other	Use of Botox within 4 month prior to SP II and during study	nonprogrammable
		Use of other excluded meds during study	Nonprogrammable
		Use of verapamil at doses higher than allowed at baseline and during study	Programmable
		Missing any scheduled or unscheduled C-SSRS	Programmable
		Missing all triplet measurements of blood pressure or pulse at any scheduled visit	Programmable
		Missing entire chemistry or hematology panel	Programmable
		No ECG measurements during a study phase	Programmable
Investigational Product	Patient took medication not fit for use		Nonprogrammable
	Unblinding		NonProgrammable
	Other	IP lost or stolen	Nonprogrammable
		Dose planned but not given—date of injection missing	Programmable
		Dosing interval outside specified limits of 21-37 days for double-blind treatment phase	Programmable
Safety	SAEs		Nonprogrammable
	Other	Positive pregnancy test	Nonprogrammable
Data Quality	Treatment Assignment/Randomization Error	IWRS data entry errors that impact patient stratification	Programmable
	Treatment Assignment/Randomization Error	Randomized after screening failure, no study drug dispensed	Programmable

Category	Subcategory	Study Specific Term	Source
Data Quality	Other	Primary efficacy compliance rate $\leq 50\%$ in any weekly interval during DB treatment phase	Programmable
	Data Entry Issues	Patients did not report oxygen use in number of times in eDiary	nonprogrammable
Administrative Oversight	Patient Privacy Violation		Nonprogrammable
	Suspected Misconduct		Nonprogrammable
	Other	Post training; switching roles blinding to unblinded vice versa without prior medical team approval	Nonprogrammable
		Unqualified or untrained site personnel administer (C-SSRS)	Nonprogrammable
		Quality issue at site or vendor	Nonprogrammable

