execute the eligibility report). If the patient is eligible, a blinded randomization authorization code will be listed for the patient. The site personnel, either blinded or unblinded, must log into the Eli Lilly Interactive Web Response System (IWRS) to process the patient's randomization visit (Visit 3). The site should discontinue the non-eligible patient in the IWRS system at Visit 3. For patients that are eligible for randomization, the site should enter the randomization authorization code provided by the vendor.

Only the Unblinded Site Personnel should confirm the assigned packages in IWRS. The Unblinded Site Personnel should store the randomization authorization code from the vendor for each patient in a secure pharmacy record for the study.

SP III is an 8-week randomized, double-blind, placebo-controlled treatment phase. Patients who meet all eligibility criteria will be randomized to LY2951742 300 mg or placebo. The unblinded site personnel will prepare the IP for each patient. Each dose of IP will be administered as 3 SC injections at office visits Visit 3 and Visit 5. After the first administration of IP at V3, the patient should remain in the office for 30 minutes for observation. The site will have a scheduled phone visit (Visit 4 and Visit 6) with the patient approximately one week after each IP administration to collect spontaneously reported AEs. During SP III, the patient will continue to record their cluster headache attack information daily in the ePRO diary.

Study Phase IV is a 16-week post-treatment phase for safety follow-up. Patients who discontinue early in SP III should enter the post-treatment phase (SP IV).

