9.1. Treatments Administered

This study includes 2 treatment groups: placebo or LY2951742 300 mg. Each treatment group will be administered three 1 ml SC injections, by qualified site personnel, every 30 days for a total of 2 administrations during SP III. The designated unblinded site personnel responsible for preparing LY2951742 and placebo doses should refer to the Pharmacy Binder Dosing Instructions for LY2951742 Drug Product, 75 mg, for the preparation and dosing instructions for both LY2951742 and placebo.

The investigator or his/her designee is responsible for the following:

- explaining the correct use of the investigational agent(s) to the site personnel,
- verifying that instructions are followed properly,
- maintaining accurate records of investigational product dispensing and collection, and
- returning all unused medication to Lilly or its designee at the end of the study.

Note: In some cases, sites may destroy the material if, during the investigator site selection, the evaluator has verified and documented that the site has appropriate facilities and written procedures to dispose clinical trial materials.

Possible injection sites include the abdomen, thigh, and upper arm. Buttocks may also be used, if more appropriate for SC injection than the other sites.

Patients will be instructed to contact the investigator as soon as possible if he or she has a complaint or problem with the IP so that the situation can be assessed.

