9.8. Concomitant Therapy

Patients will be allowed to use only the following acute/abortive treatments for their cluster headache attacks: high-flow oxygen; oral triptans, sumatriptan SC injections; sumatriptan nasal spray; zolmitriptan nasal spray; acetaminophen; NSAIDs. No medications, treatments, procedures, or other interventions for the preventive treatment of cluster headache are permitted during SP II and SP III. In SP IV, if the investigator deems it necessary to resume a preventive medication for a patient, the patient is allowed to resume only the following medications for prevention of cluster headache: verapamil (maximum daily dosage: 480 mg), lithium, melatonin, valproate, gabapentin, and topiramate. Patients will be asked to record use of their allowed standard abortive treatments in their daily ePRO diary.

A list of allowed/not allowed medications will be provided separately. Site personnel should call a designated Lilly representative with any questions regarding medications not specifically cited in the list of allowed/not allowed medications. Any changes in the list of allowed/not

allowed medications will be communicated to investigators and will not constitute a protocol amendment.

Patients should be instructed to consult with the investigator or study coordinator at the site before taking any new prescribed medications, over-the-counter (OTC) medications, or supplements. If the need for other concomitant medication arises, inclusion or continuation of the patient in the study may be at the discretion of the investigator after consultation with CRP/CRS or delegate.

10. Efficacy, Safety Evaluations, Sample Collection and Testing, and Appropriateness of Measurements

Study procedures and their timing (including tolerance limits for timing) are summarized in the Study Schedule ([Attachment 1](#)).

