Attachment 1. Protocol CGAL Study Schedule

Study Schedule, Protocol I5Q-MC-CGAL, SP I - SP III

Patient Status	Entering in active cluster period	Entering in Remission		SP III					Comments
		SP I	SP II	Treatment					
Study Phase (SP)	Screening/ Pre-Rand. Diary	Screening	Pre-Rand. Diary	3	4 (Ph. visit)	5	6 (Ph. visit)	7	Comments
Description	1 (Note: V1 and V2 procedures are combined into V1)	1	2	3	4 (Ph. visit)	5	6 (Ph. visit)	7	
Visit	Min range: SP I/II-10 to 15d	Allowable range b/w V1 and V2: 0 d to 1 yr	Min range: SPII-10 to 15d; V2 to V3-5d	3	4 (Ph. visit)	5	6 (Ph. visit)	7	Phone visits (V4 and V6) are contacts between office visits to collect any spontaneously reported AE
Visit Day									For flow of patients through SP I and SP II, please refer to the study design Section 7.1.
Month				Day 1	Day 7	Day 30	Day 37	Day 60	
Interval (days) since previous office visit						1		2	
Interval allowance (days)					7	30	7	30	The interval from V3 to V5 and the interval from V5 to V7 should be no less than 28 days .
					+/-1	+5/-2	+/-1	+5/-2	
Informed consent	X	X							Patients who have an extended period between V1 and V2 may need to be re-consented according to local regulations. Sites will be encouraged to stay in contact with patients during SP I who enter in remission.
Inclusion and exclusion criteria	X	X	X	X					
Dispense ePRO diary	X	X							
Demographics	X		X						
Med history and pre-existing conditions	X	X							

Study Schedule, Protocol I5Q-MC-CGAL, SP I - SP III

Patient Status	Entering in active cluster period	Entering in Remission		SP III Treatment					Comments
		SP I	SP II						
Study Phase (SP)	Screening/ Pre-Rand. Diary	Screening	Pre-Rand. Diary						
	1 (Note: V1 and V2 procedures are combined into V1)	1	2	3	4 (Ph. visit)	5	6 (Ph. visit)	7	
Visit									
Treatment				X		X			IP injections are to occur after all other visit procedures are completed. Following the first dose at V3 , patients will be observed for 30 min in the office
Prior cluster headache attack history	X	X							
ECG	X		X					X	All ECGs should be collected prior to blood draws and dosing. Patients must be supine for approx. 5-10 min before ECG collection and remain supine but awake during ECG collection
Physical examination	X	X	X						Must include a brief neurological exam
Caffeine use	X		X						
Tobacco use (smoking and non-smoking)	X		X						
Nicotine use	X		X						
Alcohol use	X		X						
Height	X	X	X						
Weight	X	X	X					X	

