5.5.3. Important Protocol Deviations

Important protocol deviations that potentially compromise the data integrity and patients' safety will be summarized by treatment for the ITT population.

Section 7 (appendix) lists the categories, subcategories, study-specific terms of important protocol deviations, and source of identification. Per study team's discretion, for non-programmable protocol deviation, additional categories and subcategories other than the ones on Section 7 can always be added into the final nonprogrammable protocol deviations list as deemed necessary.

Tables and listings of subjects with important protocol deviations will be provided for the ITT population.

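### Does the SAP's 21–37 day dosing-interval limit conflict with the protocol's 28–35 day visit window?

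*SAP*

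**What the plan says.** **Dosing schedule.** Protocol 9.1 has both arms injected "every 30 days for a total of 2 administrations during SP III", and Protocol 7.1 places the doses: "Each dose of IP will be administered as 3 SC injections at office visits Visit 3 and Visit 5". In Protocol Attachment 1 the Visit 5 column shows an interval of 30 days with an allowance of +5/−2, and the comment column adds: "The interval from V3 to V5 and the interval from V5 to V7 should be no less than 28 days".

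**Deviation list.** SAP 5.5.3 restricts the list to deviations with the potential to compromise data integrity and patient safety, and refers to Appendix 1 for the categories. Its stated use is descriptive: "Tables and listings of subjects with important protocol deviations will be provided for the ITT population". It leaves room to extend the list, but in these terms: "for non-programmable protocol deviation, additional categories and subcategories other than the ones on Section 7 can always be added". The dosing row in Appendix 1 reads "Dosing interval outside specified limits of 21-37 days for double-blind treatment phase" and is marked as programmable.

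**Verapamil.** Another programmable row reads "Use of verapamil at doses higher than allowed at baseline and during study". Protocol 9.8 says: "No medications, treatments, procedures, or other interventions for the preventive treatment of cluster headache are permitted during SP II and SP III". The same section gives a maximum daily verapamil dosage of 480 mg for SP IV and refers to a separately supplied list of allowed and disallowed medications. Inclusion criterion 9a bars verapamil in the 14 days before SP II, and Appendix 1 has its own row for breaches of 9a through SP III.

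**The concern.** The row speaks of specified limits, but neither document specifies 21 to 37 days anywhere else, and the only dosing window they do give is narrower. The numeric eligibility rows in the same appendix (QTcB, blood pressure, BMI, baseline diary days, the 14- and 30-day washouts) repeat the protocol's limits. A reader could therefore take 21–37 to be the protocol window as well. Some second doses given outside the visit window would then be absent from the deviation tables, and adherence to the schedule would look better than it was. The provision for adding categories covers only non-programmable deviations, so it offers no obvious route to repair a programmed row.

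The verapamil row raises the same kind of doubt: it refers to an allowed dose at baseline, although the protocol permits no preventive treatment in SP II or SP III.

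At stake is the completeness and clarity of one descriptive table. The question is whether anything beyond that table is affected.

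**Working it through.** **1. The protocol window.** Inputs: interval 30 days, allowance +5/−2, floor 28 days (Protocol Attachment 1).

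- Lower limit: 30 − 2 = 28 days, which agrees with the stated floor.
- Upper limit: 30 + 5 = 35 days.

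**2. Can 21–37 be reproduced?** The SAP limits are 30 − 9 = 21 and 30 + 7 = 37. The Visit 5 allowance gives 28–35, and a symmetric ±7 days gives 23–37. No allowance stated for the dosing visits yields 21–37.

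**3. What the row leaves out.**

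- Below the window: 21 to 27 days, 28 − 21 = 7 values.
- Above the window: 36 and 37 days, 37 − 35 = 2 values.
- Total: 7 + 2 = 9 whole-day values.
- Dosing intervals per patient: 2 administrations − 1 = 1, so at most one unreported entry each.

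**4. Does the interval reach the endpoints?** SAP 5.4.1.2 counts the first injection as Day 1, takes Days 1–21 as Weeks 1–3, and ends Week 4 on the day before the second injection. An interval of d days puts the second injection on Day d + 1, so Week 4 has d − 21 days. As a check, Week 4 has 13 calendar days in both examples of Table CGAL.5.1; 13 + 21 = 34 days, which is inside 28–35.

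| Interval (days) | Days in Weeks 1–3 | Days in Week 4 | Flagged by SAP row |
|---|---|---|---|
| 20 | 20 | 0 | yes |
| 21 | 21 | 0 | no |
| 24 | 21 | 3 | no |
| 25 | 21 | 4 | no |
| 28 | 21 | 7 | no |
| 35 | 21 | 14 | no |
| 37 | 21 | 16 | no |

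Every unflagged interval leaves Weeks 1–3 whole. The primary analysis (Weeks 1–3) and the 50% response at Week 3 therefore keep their full diary windows. It happens that 21 is the shortest interval for which this is true. That would be a sensible reason for the lower limit, but it is an inference; the SAP does not state it.

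**5. Does the flag reach any analysis?** SAP 5.5.1.5 names three populations (ITT, safety, posttreatment), with no per-protocol set. No sensitivity analysis in SAP 5.5.11 selects patients by deviation. The flag therefore enters no estimate and no test.

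**6. Is a looser limit out of keeping with the appendix?** Diary recording is daily under the protocol, but only weekly compliance of 50% or less is listed. Blood pressure and pulse are taken in triplicate, but only the loss of all three readings is listed. For laboratory tests, only a missing entire chemistry or hematology panel is listed. The pattern is not uniform, since any missed C-SSRS is listed, but a dosing limit wider than the visit window is not an anomaly among the conduct rows.

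**7. Verapamil.** The row covers the whole study, and SP IV is part of it, so the SP IV maximum in Protocol 9.8 gives the row something to check. Only the baseline part has no matching limit in the two documents. The separate medication list is not available here, so it cannot be said that no such limit exists.

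**The case for a change.** The best case for acting is that the table should mean what it says. The eligibility rows mirror the protocol, so the words about specified limits invite the reader to assume that this row does too. There is also a practical gap. With an interval of 22–24 days, Week 4 has only 1–3 days and is set to missing by the rule on 3 or fewer diary days, even with a perfect diary. The compliance row would miss this, because 3 entries out of 3 expected is 100%. At 21 days Week 4 has no days at all. So an early second dose could remove a Week 4 value while neither row reports it. The correction would cost a footnote or one program parameter.

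The facts in this stand: 21–37 is unexplained, and the short-interval gap is real. It does not follow that the plan must change. The Week 4 value is lost because of the actual injection date and the missing-day rule; a tighter flag would not restore it. Week 4 enters neither the primary analysis nor the Week 3 response comparison. Administration dates and times are recorded for each dose (SAP 5.5.5), so every interval can be derived for the study report if someone asks. The row also prints its own numbers and does not cite the Study Schedule, so its difference from the visit window is visible.

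**Conclusion.** No change is needed. The protocol's 28–35 days governs when the visit should take place. The SAP's 21–37 days governs which departures are listed as important. Those are different questions, and SAP 5.5.3 makes the list a restricted one. What is missing is the reason for the two numbers and the source of the baseline reference in the verapamil row. Analysts and report writers can supply both from the dosing dates and the medication list.

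The size is nine whole-day interval values outside the visit window and not reported under this row, with at most one entry per patient. The documents do not show how many patients would fall there; it could be none. Whatever the number, the effect on the primary, Week 3 response, other efficacy and safety results is nil, because nothing in the SAP conditions on the flag.

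This rests on two assumptions: that the list is used only for the tables and listings described in SAP 5.5.3, and that no document outside these two turns the flag into an exclusion. If a per-protocol analysis were built on this list, the limits would need a stated basis and would have to be reconciled with the Study Schedule. Nothing here takes a view on which interval or dose is right.

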12.2. Statistical and Analytical Plans

12.2.1. General Considerations

Unless otherwise specified, efficacy analyses during SP III will be conducted on an intent-to-treat (ITT) population, which include all patients who are randomized and receive at least 1 dose of IP. Patients in the ITT population will be analyzed according to the treatment group to which they were randomized. Safety analyses during SP III will be conducted on the safety population, which also includes all patients who were randomized and receive at least 1 dose of study drug. However, patients will be analyzed by actual study treatment received most often (modal treatment) during the double-blind treatment phase. When change from baseline is assessed, the patient will be included in the analysis only if he/she has a baseline and a post-baseline measurement.

For analyses of the post-treatment phase, the post-treatment population will be used. Post-treatment population will be defined as all patients who entered the post-treatment phase (SP IV) as indicated by entering any post-treatment visit.

Details related to handling of missing data will be described in the SAP.

Treatment effects will be evaluated based on a 2-sided significance level of 0.05 for all the efficacy and safety analyses unless otherwise stated. The 95% confidence intervals (CIs) for the difference in least-square means (LSMeans) between treatment groups will be presented. Adjustments for multiple comparisons for the analyses corresponding to the primary and gated secondary objectives are described in the sections on the primary and secondary efficacy analyses below. There will be no adjustments for multiplicity for analyses of other data.

Categorical comparisons between treatment groups will be performed using Fisher's exact tests, where appropriate.

Any change to the data analysis methods described in the protocol will require an amendment ONLY if it changes a principal feature of the protocol. Any other change to the data analysis methods described in the protocol, and the justification for making the changes, will be described in the statistical analysis plan (SAP) and/or in the clinical study report.

Additional exploratory analyses of the data will be conducted as deemed appropriate.

Statistical analysis of this study will be the responsibility of Eli Lilly and Company or its designee. SAS® software will be used to perform most or all statistical analyses.

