5.5.1. General Considerations

General aspects of statistical analyses are described below.

Unless otherwise specified, efficacy analyses during SP III will be conducted on an **intent-to-treat (ITT) population**, which include all patients who are randomized and receive at least 1 dose of study drug. Patients in the ITT population will be analyzed according to the treatment group that they were randomized to. Safety analyses during SP III will be conducted on the **safety population**, which also includes all patients who are randomized and receive at least 1 dose of study drug. However, patients will be analyzed by actual study treatment received most often (modal treatment) during the double-blind treatment phase. Modal treatment will be the same as randomized treatment except in some cases of incorrect treatment administration. When mean change from baseline is assessed, the patient will be included in the analysis only if he or she has a baseline and a postbaseline measurement.

Unless otherwise specified, for analyses of posttreatment phase, the **posttreatment population** will be used. **Posttreatment population** will be defined as all patients who entered the post-treatment phase (SP IV) as indicated by entering any posttreatment visit.

Statistical analysis will be carried out for the 8-week treatment phase (SP III), the 16-week post treatment phase (SP IV) as well as the 8-week treatment and 16-week post treatment phases combined (SP III/IV) as listed in [Table CGAL.5.2](#).

Safety analyses (Section [5.5.9](#)) in SP III and SP IV and analyses for exposure will be conducted based on the modal treatment group patients have received (placebo or GMB300 mg). For determining modal treatment, if there are 2 modes, then the modal treatment group will be GMB300 mg.

Unless otherwise specified, for the analyses in SP IV alone, no statistical comparisons between any treatment groups will be conducted.

Since cluster headache attack information collected through ePROs will only be collected for SP III, analyses of ePRO data will be conducted at SP III only.

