5.5.1.5. Analysis Populations

Three analysis populations, including the ITT population, the safety population, and the posttreatment population, are defined in Section [5.5.1](#).

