5.5.2. Patient Disposition

The number and percentage of ITT patients who complete the study or discontinue early will be tabulated for all treatment groups for SP III and SP IV both overall and by visit. Reasons for discontinuation will be compared between treatment groups using Fisher's exact test for SP III with the ITT population. Descriptive statistics only will be presented for the treatment groups in SP IV. For patients who were randomized without drug injection, reasons for early discontinuation will be provided in a listing.

Patient allocation by investigator will be summarized for SP III for all ITT patients.

Patient allocation by investigator will also be listed for all SPs.

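### An important deviation defined for randomized patients who got no study drug is reported only in a dosed population, so its count is zero by construction

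*SAP*

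**What the plan says.** The list of important deviations in SAP Appendix 1 includes, under Data Quality and the subcategory for treatment assignment or randomization error, the term "Randomized after screening failure, no study drug dispensed". Its source is given as programmable.

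SAP 5.5.3 sets the population for reporting. Important deviations "will be summarized by treatment for the ITT population", and the section then repeats the restriction for the outputs themselves: "Tables and listings of subjects with important protocol deviations will be provided for the ITT population".

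SAP 5.5.1 defines ITT as a set "which include all patients who are randomized and receive at least 1 dose of study drug". Protocol 12.2.1 agrees: "which include all patients who are randomized and receive at least 1 dose of IP". The safety population carries the same condition, "which also includes all patients who are randomized and receive at least 1 dose of study drug". SAP 5.5.1.5 confirms that these two and the posttreatment population are the only sets ("Three analysis populations, including the ITT population, the safety population, and the posttreatment population, are defined in Section" 5.5.1), so there is no all-randomized population.

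One other output covers undosed patients. SAP 5.5.2 states: "For patients who were randomized without drug injection, reasons for early discontinuation will be provided in a listing".

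**The concern.** The SAP specifies a programmed check and then sends its result to a table that cannot contain a positive case. A reader who sees zero for this term would naturally take it as a finding that no such error occurred, when it only restates the population definition.

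Two features of the design make pre-dose randomization errors worth documenting.

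- Allocation is by minimization (Protocol 9.3, SAP 5.3), in which assignments depend on the patients already allocated. A patient randomized in error can therefore affect later assignments even if never dosed. The permutation test in SAP 5.5.11 re-runs the exact minimization algorithm with enrollment order held fixed, so the record of who was randomized in error bears on that analysis.
- Unblinded site staff confirm the assigned packages and prepare the dose before injection (Protocol 7.1 and 9.2). Someone at the site can therefore know the arm before the first dose. That is no evidence of selective loss, but it is a reason to show pre-dose errors by arm.

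**Working it through.** No sample-size or error-rate calculation applies, and the plan states no figure to reproduce. The check is set logic on the plan's own definitions.

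**Inputs**

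| Item | Condition | Source |
|---|---|---|
| ITT | randomized and doses ≥ 1 | SAP 5.5.1; Protocol 12.2.1 |
| Safety | randomized and doses ≥ 1 | SAP 5.5.1 |
| Deviation D | randomized and no drug dispensed | SAP Appendix 1 |
| Reporting set for D | ITT, for the summary, tables and listings | SAP 5.5.3 |

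**Step 1: no drug dispensed means no dose.** Qualified site personnel give the injections (Protocol 9.1), and patients hold no supply of their own. Hence D implies doses = 0.

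**Step 2: the reported count.** In each arm, reported count = |D ∩ ITT|. D requires doses = 0 and ITT requires doses ≥ 1, so |D ∩ ITT| = 0 for any data. The safety population would also give 0.

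**Step 3: the other terms.** For any other term T, the count in all randomized patients splits as |T ∩ (doses ≥ 1)| + |T ∩ (doses = 0)|. SAP 5.5.3 reports the first part and drops the second. This touches consent failures, eligibility violations and IWRS entry errors that affect stratification, but only in patients who were never dosed. For a planned dose that was not given, a missed second dose after a first is captured in full, because that patient is in ITT. Only a patient who received no dose at all is lost. D is the one listed term that is clearly empty by definition.

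**Step 4: is there an exception elsewhere?** None was found. The discretion in SAP 5.5.3 to add categories applies to nonprogrammable deviations and does not alter the population, and D is programmable. The posttreatment population is not used for deviation reporting. The SAP 5.5.2 listing gives reasons for discontinuation. It does not classify deviations, and no summary by arm is promised.

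**Step 5: size.** Reported for all randomized patients, the count would be |D|, which is zero or more. The documents give no number of patients randomized but not dosed, so |D| cannot be computed. The planned minimum of about 162 does not supply a denominator either, because the SAP revision history says enrollment was terminated before reaching the target for the planned interim analysis.

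**The case against.** The strongest reply is that these patients are not hidden. The SAP 5.5.2 listing should contain every patient randomized without an injection, with a reason. Protocol 12.2.2 says that all patients who discontinue will be identified, with their extent of participation and any known reason, and that sentence is not limited to ITT. Protocol 8.4.1 also requires notification between site and sponsor when an ineligible patient is enrolled, and a log entry for the decision on continuation. This reply stands. A reader might infer from the deviation table that the study report as a whole would show no erroneous randomizations, but the documents do not support that. What is missing is narrower: classification as an important deviation, and a count by arm.

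A reader might also infer that arm differences among undosed patients would be concealed. The SAP does not say whether the 5.5.2 listing carries the randomized arm, so that is not established. Counting undosed patients by arm is also partly a disposition question.

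Randomization and first dosing both take place at Visit 3, so the undosed group is plausibly very small. That is reasonable but cannot be verified from the documents, and it does not rescue a term that cannot be counted.

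Finally, moving every deviation to all randomized patients would do harm. Rules on missing C-SSRS, missing laboratory panels, absent ECGs in a study phase and low diary compliance in double-blind weeks would flag patients who were never treated. This objection also stands, and it limits the remedy.

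**Conclusion.** The inconsistency is real and minor. As written, SAP 5.5.3 makes one pre-specified deviation unreportable: its count is zero in both arms for any data. The other consent, eligibility and randomization-error terms lose only their undosed subset. The conclusion rests on reading SAP 5.5.1 and 5.5.3 as they stand, and on a patient with no drug dispensed having received no dose, which follows from injection by site personnel.

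It does not extend to the efficacy results. A reader might take it as a sign of bias in the primary comparison, but the deviation outputs do not feed the primary model and nothing here changes that estimate. The number of patients affected is unknown and could be zero.

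**What to change.** Amend SAP 5.5.3 so that the population depends on the type of deviation.

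- **All randomized patients, by randomized arm:** this term, together with the other consent, eligibility and treatment-assignment/randomization-error terms. Two eligibility terms on excluded medication also run into SP III; their post-dose part should still apply only to dosed patients.
- **ITT population, as now:** the terms that presuppose dosing, namely missing C-SSRS, missing laboratory panels, absent ECGs, diary compliance and dosing interval.

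SAP 5.5.1.5 needs a line defining the all-randomized set, since none exists.

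No new data are required. The cost is one added population flag in the deviation table and listing, and possibly a few more deviations shown.
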